5.1.2 Invitation of potential study participants to attend screening visit

The staff at each practice will identify potentially eligible participants aged 65-84 from GP practice records based on the eligibility criteria listed in section 4 (approximately 900 per practice). Each GP practice will then contact potentially eligible participants by letter (on site specific headed paper) with an accompanying participant information sheet describing the study in detail. Mailings to these potential participants will contain reply slips and pre-paid, return addressed envelopes for participants to indicate whether, having read the letter and participant information sheet, they are interested in attending the GP surgery for an enrolment visit. Eligibility of respondents will be confirmed by the local PI (GP). Respondents will then be telephoned by the practice staff to confirm eligibility and arrange a screening visit at their GP surgery, at least 24 hours after the phone call, where signed informed consent will be obtained from those agreeing to participate in the trial. It is expected that at least 9% (80 per practice) will participate.

Respondents who do not speak English fluently can bring a relative or friend to interpret when they attend the GP practice for consent and enrolment. This will be explained when the practice nurse telephones to arrange the enrolment visit if the potential participant appears not to understand English adequately. They will also be asked if they wish to be sent the patient information sheet and consent form translated into their language before attending the practice for informed consent and enrolment. Advocacy services for translation and interpreting will be used when required.

5.1.3 Enrolment / Screening visit

Informed consent: At the screening visit, the practice nurse will review the inclusion and exclusion criteria with the potential participant to verify eligibility. The nurse will then obtain written informed consent to participate in the trial, after explaining the aims,

methods, anticipated benefits and potential hazards of the study. Written informed consent will include vitamin D assays on blood samples taken during the study, and access to all written and electronic medical records and databases. Participants will also be consented to be flagged for lifelong automatic follow-up for mortality and cancer registration through the NHS Information Centre and NHS Central Register, and for hospital admissions through HES. Consent will also include permission (i) to access GP records to abstract information about infections, prescriptions and the frequency of GP visits made in the year leading up to randomisation and 2 years post randomisation; and (ii) to store their personal data centrally at the Trial Coordinating Centre for the purposes of sending trial medication and trial follow-up. Additional optional informed consent will be obtained for long-term storage of blood samples and unspecified tests (including unspecified genetic analyses) for future research, subject to further ethical approval. During the consent process, the practice nurse will explain that participants are completely free to refuse to enter the study or to withdraw at any time during the study for any reason.

Lifestyle questions, blood pressure and BMI: The online CRF will record details on quality of life, foreign holidays, sunbathing, sunbed use, ethnic origin and use of vitamin supplements, with responses from potentially eligible consented participants being recorded by the practice nurse (or trained delegate) during the enrolment visit. Participants will also have their systolic and diastolic blood pressure, height, weight and waist circumference measured and recorded. Any paper copies of the baseline visit data must be entered onto the online VIDAL app immediately afterwards to allow automated eligibility checks to be performed without delay.

Blood samples: Participants will also be asked to give 12.5 ml of blood (9 ml lithium heparin vacutainer and 3.5 ml SST vacutainer). The 3.5 ml aliquot of blood will be sent by the practice to their local laboratory for corrected serum calcium assay to establish trial eligibility prior to randomisation. The 9 ml aliquot of blood will be sent to the Clinical Trials Service Unit in Oxford for separation of buffy coat, assay of circulating 25(OH)D level (assay performed at the end of the study), and long term storage of buffy coat and plasma (as 3 aliquots) in liquid nitrogen. Subsequent genetic and other analyses, if funded, may include common variants of the vitamin D receptor and vitamin D binding protein genes, alterations such as DNA methylation and telomere length, and more extensive blood chemistry, including serum creatinine at entry and 2 years to assess the effect of vitamin D on renal function.

5.1.4 Assessment of Eligibility by Trial Coordinating Centre

The signed informed consent will be retained by the GP practice, and a copy will be sent by the practice to the Trial Coordinating Centre. The Trial Coordinating Centre (and automated VIDAL app) will confirm participant eligibility by (i) checking that the signed informed consent is satisfactorily completed, (ii) checking that the corrected serum calcium result has been entered on the website and is no higher than 2.65 mmol/L and, (iii) checking that the online lifestyle questions have been satisfactorily completed for each participant. Participants will then be telephoned by the Trial Coordinating Centre to confirm their eligibility and check that they are still willing to participate in the trial. The participant will then be randomised. Participants found to be ineligible because of hypercalcaemia (i.e. with a baseline corrected serum calcium > 2.65 mmol/L) will be advised during the phone call that the GP practice will be in contact to discuss whether any treatment is indicated.

5.1.5 Randomisation Procedures

Cluster randomisation of GP practices:

Before the study starts the 20 participating GP practices will be matched in pairs on region and social mix (deprivation index of the Ward of the GP practice based on the GP practice postcode). They will then be randomised, one to the blinded study and one to the open control study, within each pair by the VIDAL app.

Individual randomisation of eligible participants within the practices:

The VIDAL app will generate a random sequence of allocations for each practice balanced in blocks of 6 or 8 so that the next participant's allocation cannot be predicted but succeeding allocations maintain a 1:1 ratio of vitamin D or control within each practice.

The Royal London Hospital pharmacy will hold the medication packs, labelled with a pack code according to Good Manufacturing Practice (GMP) principles. Packs for open control practices will all contain open label vitamin D. Packs for blinded practices will identify the contents as "vitamin D₃ oil / placebo oil". The allocated treatment can be determined from the pack code from a master list supplied by the manufacturer. This will be entered onto the online CRF (VIDAL app), but access will be restricted to independent trialists at The Cancer Prevention Trials Unit at Queen Mary University of London who will hold copies for the purpose of unblinding.

After checking eligibility and telephoning the participant to confirm consent (see 5.1.4 above) the Trial Coordinating Centre will instruct the VIDAL app to randomise and to issue the next available pack code for the randomly allocated treatment, unless it is open control (i.e. no treatment). Participants allocated to open control will receive a letter from the Trial Coordinating Centre explaining that they will be re-contacted at 2 years for a follow-up visit and further blood sample. For all other participants (open-label vitamin D. blinded vitamin D, placebo control) the VIDAL app will produce a covering letter addressed to the participant and a prepaid return slip carrying the participant's name, study ID and allocated pack code for the first year of treatment. The VIDAL app will also send an electronic prescription to the clinical CI or a delegated clinician, who will print and sign the prescription and either take it directly to the pharmacy, or return it to the Trial Coordinating Centre. If the latter, the Trial Coordinating Centre will forward signed prescriptions to the pharmacy in batches. A member of the Trial Coordinating Centre staff will attend the pharmacy approximately weekly to send by recorded delivery the covering letter, prepaid return slip and allocated medication pack to the participants. Participants will be asked to confirm receipt and pack code and record the date when their first dose of study oil was taken by posting the return slip in the reply-paid envelope to the Trial Coordinating Centre. Participants will also be asked to record the date each dose of study oil is taken (from month 1 to 12) on the front of the treatment pack. The participant will be telephoned two weeks later by the Trial Coordinating Centre if confirmation of delivery has not been received.

A year later the VIDAL app will issue the next available pack code for the allocated treatment, and the second year's medication will be sent by the same procedure.

Participants will be asked to retain both treatment packs (for year 1 and year 2) and bring them along to the final (2-year) visit to the GP practice for the purpose of returning unused doses of study oil and confirming the date each dose of oil was taken (as recorded by each participant on the outside of the treatment packs).

5.2 UNBLINDING

A list of all randomised participants specifying name, sex, date of birth, practice, allocated treatment and corresponding pack code(s), will be accessible from the online CRF (VIDAL app) by independent trialists at The Cancer Prevention Trials Unit at Queen Mary University of London, to enable them to break the code if clinically necessary, but will not be accessible by any VIDAL Trial personnel. Specified staff at The Cancer Prevention Trials Unit at Queen Mary University of London will also be given a copy of the file provided by Nova Laboratories specifying the pack codes and contents (whether vitamin D or placebo) of all treatment packs. As this is a study of a micro-nutrient at a dose below the tolerable upper intake limit, 24-hour unblinding is not necessary.

A GP or the sponsor may request an emergency code break in the following circumstances:

- a) In case of a suspected serious adverse reaction (SAR or SUSAR) where knowledge of participant allocation may influence clinical management of a study participant.
- b) In any other circumstance in which the GP or clinical CI considers that an emergency code-break is indicated.

6. TREATMENTS

6.1 TREATMENT ARMS

6.1.1 Definition of each IMP

IMP will be manufactured, supplied, labelled (description and pack code) and packaged by Nova Laboratories Ltd. according to principles of GMP. The packs and each bottle will be labelled as "vitamin D₃ oil / placebo oil" for the blinded practices and as "vitamin D₃ oil" for open control practices. An additional label on the treatment pack will have 12 spaces for the participant to record the date when each monthly dose was taken.

Active drug

Trade name: Vigantol® Oil

Composition: 0.5 mg vitamin D₃ /ml in Miglyol® 812 vehicle oil

ATC code: A1 1 CC05 (cholecalciferol)

Pharmaceutical form: Oily solution

Dosage regimen: 24 x 5 ml (= 24 x 2.5 mg) over two years

Route of administration: Oral

Manufacturer Merck Serono GmbH

[name]

Germany

Placebo

Trade name: Miglyol® 812 Oil

Composition: A pharmacopoeia-listed mixture of palm oil and coconut oil

containing medium chain triglycerides that is used as the excipient for vitamin D₃ in Vigantol® Oil; it is thus identical to Vigantol® Oil in every respect (except for the absence of

vitamin D3).

ATC code: Not applicable Pharmaceutical form: Oily solution

Dosage regimen: 24 x 5 ml over two years

Route of administration: Oral

Manufacturer Caesar & Loretz GmbH

[name]

6.1.2 Product sourcing, manufacture and supply

Authorisation number: MIA(IMP) 13581

Authorisation holder: Nova Laboratories Ltd., [name]. A named pharmacist in the Royal London Hospital pharmacy will be the recipient.

6.1.3 Treatment supply and dose

Blinded (placebo control) practices: Nova Laboratories Ltd. will prepare packs each containing 12 monthly doses of medication labelled as "vitamin D3 oil / placebo oil" and carrying a unique pack code. One will be issued at randomisation, and one year later participants will be sent a second pack containing the same medication. Each pack will contain either 12 bottles each containing 5 ml Vigantol® Oil (oily solution of vitamin D3, concentration 0.5 mg/ml) or 12 bottles, each containing 5 ml Miglyol® 812 oil (placebo). Nova Laboratories Ltd will be responsible for generating a random sequence of pack codes balanced in blocks of 10 to order the labelling of the packs so that succeeding pack codes maintain a 1:1 ratio of vitamin D or placebo. (This is for the convenience of the pharmacy, where packs will be ordered by pack code. Participants will be independently randomised by the VIDAL app – see section 5.1.5 above.) The next unallocated blinded pack code for a participant's allocated treatment will be issued by the VIDAL app, both for the first year of treatment when a participant is randomised, and a year later for the second year.

Open control practices: Nova Laboratories Ltd. will prepare packs each containing 12 monthly doses for participants allocated to vitamin D, labelled as "vitamin D₃ oil" and carrying a unique pack code. One will be issued at randomisation, and one year later participants allocated to vitamin D will be sent a second pack. Each pack will contain 12 bottles each containing 5 ml Vigantol® Oil (oily solution of vitamin D₃, concentration 0.5 mg/ml). The next unallocated open label pack code will be issued by the VIDAL app, both for the first year of treatment when a participant is randomised to open label vitamin D, and a year later for the second year.

2,000 treatment packs for blinded practices and 1,000 for open control practices will be supplied, providing 25% spare capacity to allow for exceeding the recruitment target and for replacing lost packs.

6.1.4 Treatment procedure

IMP will be presented as 5 ml oily solution that can be swallowed. It may be mixed with fruit juice or soaked into bread to aid palatability.

6.2 DOSE MODIFICATIONS FOR TOXICITY

6.2.1 Dose modification / reduction / delay

Administration of IMP may be delayed if a participant experiences symptoms of hypercalcaemia, pending investigation (see section 8). Doses of IMP may be administered up to two weeks before or after the scheduled date of administration.

Administration of IMP will be discontinued in the following circumstances:

- 1. If a participant develops hypercalcaemia confirmed on two blood samples as in section 8
- 2. If a participant develops a condition which requires treatment with a prohibited concomitant therapy (see section 4.3)
- 3. If a participant develops a condition which, in the judgement of an investigator, adversely affects that participant's safety, compliance or ability to complete evaluations
- 4. If an investigator concludes that this course of action is in the participant's best interests.

Participants who discontinue the study drug for any reason should not be considered to have withdrawn from the study, and will be invited to attend the practice for the final assessment and blood sample at 24 months.

6.2.2 Toxicity profiles

The toxicity profile of vitamin D₃ is reviewed in the summary of product characteristics (SmPC). This will be reviewed annually and updated if relevant new data come to light.

6.3 PREMEDICATION

Not applicable.

6.4 INTERACTION WITH OTHER DRUGS

Individuals taking carbamazepine, phenobarbital, phenytoin, primidone, digoxin, or the combination of a thiazide diuretic (e.g. bendrofluazide, metolazone) with a calcium supplement will not be eligible to participate in the study.

6.5 DISPENSING AND ACCOUNTABILITY

6.5.1 Prescription of IMP

Trial delegation logs will specify the names of physicians authorised to prescribe IMP for this study.

6.5.2 Preparation and Administration of IMP

IMP will be prepared by Nova Laboratories Ltd, and shipped to the Royal London Hospital pharmacy. Storage procedures are outlined in the SmPC. The Trial Coordinating Centre will liaise with the Royal London Hospital Pharmacy to send by recorded delivery a covering letter, prepaid reply slip and a twelve month (12 bottle) supply of IMP to the participant, recording the participant details and pack code. Participants will be asked to confirm receipt, confirm the pack code and record the date the first dose of study medication was taken to the Trial Coordinating Centre by returning the prepaid response. Participants will also be asked to record the date each dose of study oil is taken (from month 1 to 12) on the front of the treatment pack. The participant will be telephoned two weeks later by the Trial Coordinating Centre if confirmation of delivery has not been received.

The same procedures will be followed when the second year's medication is sent. When a participant mislays their medication the procedure is similar, except (1) the letter to the participant will state that it is a replacement, and (2) the treatment pack will only contain the bottle(s) of IMP required to complete the current year's treatment.

6.5.3 Labelling of IMP

IMP for open control GP practices will all contain open label Vigantol oil (vitamin D). In the double-blind placebo-controlled GP practices, with neither participant nor investigator being aware of a participant's allocation, active and placebo IMP will have identical packaging, labelling and appearance. The 12 bottles in each treatment pack will be labelled month 1, month 2 etc, and participants will record the date on which each monthly dose was taken on a label on the front of the treatment pack.

7. SAFETY REPORTING

7.1 **DEFINITIONS**

Adverse Event (AE): any untoward medical occurrence in a participant or clinical trial subject administered a medicinal product and which does not necessarily have a causal relationship with this treatment. An AE can therefore be any unfavourable and unintended sign (including an abnormal laboratory finding), symptom, or disease temporally associated with the use of an investigational medicinal product (IMP), whether or not considered related to the IMP.

Adverse Reaction (AR): all untoward and unintended responses to an IMP related to any dose administered. All AEs judged as having a reasonable causal relationship to a medicinal product qualify as adverse reactions. The expression reasonable causal relationship means that there is evidence to suggest a possible, probable or definite causal relationship (see section 7.2 below).

Unexpected Adverse Reaction: an AR, the nature or severity of which is not consistent with the applicable product information (e.g. investigator's brochure for an unapproved investigational product or SmPC for an authorised product). When the outcome of the adverse reaction is not consistent with the applicable product information this adverse reaction should be considered as unexpected. Side effects which occur in a more severe form than anticipated are also considered to be unexpected.

Serious Adverse Event (SAE) or Serious Adverse Reaction (SAR): any untoward medical occurrence or effect that at any dose

- Results in death
- Is life-threatening refers to an event in which the participant was at risk of death at the time of the event; it does not refer to an event which hypothetically might have caused death if it were more severe
- Requires hospitalisation, or prolongation of existing inpatients' hospitalisation
- Results in persistent or significant disability or incapacity

Medical judgement should be exercised in deciding whether an AE/AR is serious in other situations. Important AE/ARs that are not immediately life-threatening or do not result in death or hospitalisation but may jeopardise the participant or may require intervention to prevent one of the other outcomes listed in the definition above, should also be considered serious.

Suspected Unexpected Serious Adverse Reaction (SUSAR): any suspected adverse reaction related to an IMP that is both unexpected and serious. In this case the event is not outlined in the Summary of Product Characteristics (SmPC) or Investigator's Brochure (IB) for that product.

7.2 ASSESSING CAUSALITY

The assignment of causality should be made by the local Principal Investigator responsible for the care of the participant (the GP) using the definitions in the table below. Serious adverse events and reactions (whether expected or not) will subsequently be reviewed by the Sponsor / Clinical Chief Investigator.

| Relationship | Description | | | | | | |
|--------------|--|--|--|--|--|--|--|
| Unrelated | There is no evidence of any causal relationship | | | | | | |
| Unlikely | There is little evidence to suggest there is a causal relationship (e.g. the event did not occur within a reasonable time after administration of the trial medication). There is another reasonable explanation for the event (e.g. the participant's clinical condition, other concomitant treatment). | | | | | | |
| Possible | There is some evidence to suggest a causal relationship (e.g. because the event occurs shortly (within 24 hours) after administration of the trial medication). However, the influence of other factors may have contributed to the event (e.g. the participant's clinical condition, other concomitant treatments). | | | | | | |
| Probable | There is evidence to suggest a causal relationship and the influence of other factors is unlikely. | | | | | | |
| Definite | There is clear evidence to suggest a causal relationship and other possible contributing factors can be ruled out. | | | | | | |

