7.3.1 Recording ARs, SARs, SUSARs and other SAEs

All serious adverse events and all adverse reactions will be detected by three procedures:

- The GP or practice nurse records a serious adverse event or an adverse reaction via the online CRF (VIDAL app) as a result of routine clinical contact with the participant.
- Hospital admissions, cancer diagnoses and deaths will be identified automatically through the Hospital Episodes Statistics (HES) system and the NHS Information Centre.
- 3. Hospital admissions for at least one night will also be independently ascertained from all participants except those allocated to open control through their 3-monthly follow-up replies.

In view of the low-risk nature of vitamin D supplementation, only serious adverse events (whether or not causally related, i.e. SAE, SAR or SUSAR) and suspected non-serious adverse reactions (potentially causally related non-serious event, ie AR) will be recorded

by the GP or practice nurse in the safety section of the online CRF (VIDAL app). The criterion for recording an adverse reaction is that there is a reasonable possibility (ie evidence to suggest) that the IMP caused it. Non-serious adverse events deemed unlikely to have a causal relation to the IMP used in this study should not be recorded on the online CRF. Pre-planned hospitalisations (i.e. planned prior to randomisation) and elective treatments of a pre-existing condition do not need to be reported.

Depending on the nature of the reaction or event, the recording and reporting procedures below should be followed. Any questions concerning the reporting of SAEs and ARs should be directed to the Trial Coordinating Centre in the first instance. A flowchart is given in appendix 2 to aid with safety reporting.

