7.3.2 Non-serious Adverse Reactions (ARs)

Non-serious adverse reactions (i.e. potentially causally-related adverse events), whether expected or not, should be recorded by the GP practice in the adverse reaction section of the online CRF (VIDAL app). The GP can use the table in section 7.2 above to aid in assessing whether an adverse event should be classed as an adverse reaction: events classed as definitely, probably or possibly related to the IMP should be classed as adverse reactions. The Trial Coordinating Centre will receive automatic notification of all new entries through the online CRF. Non-serious adverse reactions do not require any further reporting.

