8. ASSESSMENT AND FOLLOW-UP

All study participants allocated to active treatment or placebo will be contacted at least once a month post-randomisation as outlined below. Those on open control will be contacted only at 24 months. The online CRF (VIDAL app) will send weekly reminders to each GP practice, listing all randomised participants with scheduled or overdue quarterly contact. The Trial Coordinating Centre will monitor adverse events, compliance and change of address online and telephone practices to give appropriate reminders.

Automated phone call, e-mail or text message every month from months 1 to 24:

All participants except those randomised to open control (no treatment) will be reminded to take their study medication every month by automated phone call, e-mail or text message generated by the online VIDAL app. No reply will be required from participants.

E-mail or letter follow up at months 3, 6, 9, 12, 15, 18, 21 and 24:

All participants except those randomised to open control (no treatment) will be contacted quarterly by e-mail or post (participant choice of medium) by the GP practice requesting a short reply by the same medium to record the dates on which the last 3 doses of study medication were taken or report reasons for non-compliance, to report any/no planned change of address, and to report any hospital admissions. The 3-monthly follow-up includes a reminder for participants to contact their GP if they are experiencing ongoing symptoms of hypercalcaemia (persistent nausea, vomiting, thirst, passing excessive amounts of urine or feeling generally unwell). All non-responders will be sent one reminder 3 weeks later and then telephoned by the GP practice staff if they have still not replied. Electronic responses will be recorded onto the VIDAL app by participants via a web-link supplied in the e-mail. Postal responses will be entered by the practice nurse on to the VIDAL app, and reminders will automatically be generated for outstanding items.

GP practice visit at month 24:

A repeat blood sample (9 ml lithium heparin vacutainer), blood pressure measurement, and responses to the same lifestyle questions will be obtained 24 months after randomisation for all 1600 participants to quantify differences in vitamin D status (circulating 25(OH)D level) between the intervention and control groups in the blinded and open-label studies.

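### The causality table's only numeric timing example, 24 hours after a dose, fits a monthly regimen poorly and may discourage recording of delayed non-serious reactions

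*Protocol*

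**What the plan says.** Section 7.2 asks the GP to assign causality "using the definitions in the table below". Two of the five rows mention timing:

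- *Possible*: there is some evidence of a causal link, for example "because the event occurs shortly (within 24 hours) after administration of the trial medication". The row adds that other factors may have contributed.
- *Unlikely*: one example is that "the event did not occur within a reasonable time after administration of the trial medication". No number is attached. The same row also refers to little evidence of a causal link and to another reasonable explanation.

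*Probable* has no timing element ("There is evidence to suggest a causal relationship and the influence of other factors is unlikely"), and neither has *definite*.

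The rating has consequences. Section 7.3.2 says that "events classed as definitely, probably or possibly related to the IMP should be classed as adverse reactions". Section 7.3.1 says that "Non-serious adverse events deemed unlikely to have a causal relation to the IMP used in this study should not be recorded" on the online CRF. Serious events are recorded whatever their causality (7.3.1) and are reviewed after the GP by the sponsor or clinical chief investigator (7.2). Only SUSARs are expedited (7.3.4). Other serious events go into the annual safety report (7.3.3).

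The regimen is 24 doses over two years (6.1.1), described in section 3 as an average of 3300 IU per day. Section 8 has participants reminded every three months to contact their GP about "ongoing symptoms of hypercalcaemia (persistent nausea, vomiting, thirst, passing excessive amounts of urine or feeling generally unwell".

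**The concern.** A 24-hour example suits an acute reaction to a dose. Here the dose is monthly, the Protocol treats it as equivalent to a daily intake, and the symptoms it asks participants to watch for are persistent. Nothing in sections 3.3 or 8 links those symptoms to the day of a dose. The *unlikely* row leaves a reasonable time undefined, so 24 hours is the only benchmark the table gives a GP who wants one.

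What is at stake is the capture of non-serious reactions. The Study Summary lists the incidence of both severe and minor adverse events as an outcome, and section 2.2(ii) aims for unbiased adverse-event data for vitamin D against placebo. If the example tips a delayed or cumulative non-serious effect from *possible* to *unlikely*, the event leaves no trace as a suspected reaction. For serious events the question is narrower: whether they are classed as suspected reactions and so could qualify as SUSARs.

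**Working it through.** The plan gives no figure for this point. There is one piece of arithmetic; the rest is a comparison of sections.

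**1. How well the example fits the regimen**

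- Inputs: 24 doses over two years (6.1.1); a window of 1 day after a dose (7.2); two years = 2 × 365.25 = 730.5 days.
- Dosing interval: 730.5 / 24 = 30.4 days.
- The Protocol's daily equivalent: 24 × 100,000 IU / 730.5 days = 3,285 IU per day, which agrees with its rounded 3300.
- Share of treatment time within 24 hours of a dose: 24 × 1 / 730.5 = 3.3%. The remaining 96.7% lies outside the only numeric window in the table.

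An event whose timing is unrelated to dosing would meet the example about 3.3% of the time. That describes the example. It says nothing about how GPs would rate events.

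**2. Reading the table for an event 15 days after a dose**

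- *Possible* is open: the 24 hours follow an e.g., and other evidence can support the rating.
- *Probable* and *definite* are open: neither has a time element.
- *Unlikely* is open if the GP thinks 15 days is not a reasonable time. The table gives no guidance on that apart from the 24 hours in the next row.

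The table therefore does not force a rating, but its one number points towards *unlikely*.

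**3. Whether another criterion overrides the example**

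Section 7.3.1 sets the test for recording a reaction as a reasonable possibility, with no time limit. However, section 7.1 explains a reasonable causal relationship through the possible, probable and definite categories and refers to 7.2. Section 7.3.2 again offers the 7.2 table as an aid. The broader criterion leads back to the same table.

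**4. What follows from a rating of *unlikely***

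- *Non-serious events other than hypercalcaemia*: not recorded on the CRF (7.3.1). The central review in 7.2 covers serious events only. The quarterly contact collects dose dates, reasons for missed doses, address changes and admissions (8). The GP-note summaries cover visits, prescriptions and infections (8). None of these recovers the event as a suspected reaction.
- *Hypercalcaemia*: reported symptoms lead to a blood test, and a raised result is repeated (8). GPs are to report hypercalcaemia as a suspected reaction, with no time window (3.3). This route does not depend on the table's timing example.
- *Serious events*: recorded regardless of causality, with admissions, cancers and deaths also found through national records (7.3.1). Comparisons for the DMC use serious adverse events without a causality filter (9.3.3, 12.1.2). What the rating can change is whether the event counts as a suspected reaction, on which SUSAR status depends (7.1, 7.3.4). Section 7.2 provides for central review but does not say whether that review can raise the GP's rating.

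**The case against.** The strongest reply is that the 24 hours only illustrate one kind of evidence. A GP remains free to decide what a reasonable time is for a monthly dose, and late onset alone does not meet the full description of *unlikely*, which also mentions another explanation. Section 7.3.2 says the GP can use the table, which is weaker than an instruction. The planned between-arm safety comparison in section 3.1.2(iii) is of serious events, which the table does not filter, and section 7.3.1 limits non-serious recording deliberately because the product is considered low risk.

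Most of this stands, and it rules out some stronger conclusions. A reader might infer that onset within 24 hours is a requirement for *possible*; the e.g. shows that it is not. A reader might infer that serious delayed events are lost or can never become SUSARs; they are recorded and reviewed centrally. A reader might take the 96.7% as the share of reactions that would be missed; that would need uniform onset and an example applied as a strict cut-off, and the Protocol supports neither.

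The reply does not explain why the one number in a table whose entries section 7.2 calls definitions should be one that fits the regimen so poorly. Nor does it provide any other capture of a delayed non-serious reaction once it is rated *unlikely*.

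**Conclusion.** The point holds as a matter of wording with a limited but real consequence. The only numeric timing example in section 7.2 covers 3.3% of treatment time on a monthly regimen and sits badly with the daily-equivalent description of the dose and the persistent symptoms in section 8. It may lead GPs to under-record delayed or cumulative non-serious effects other than hypercalcaemia, an outcome the Study Summary lists. For serious events only the suspected-reaction classification could be affected, subject to central review.

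The size of any under-recording cannot be derived from the Protocol. The conclusion assumes that some GPs would use the 24 hours as a benchmark. It also assumes that the online form and the Appendix 2 flowchart, whose content on timing is not visible here, do not already correct it. No sample size, power or other statistical figure changes. This is a cheap improvement and not a flaw in the design.

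**What to change.** - Delete the 24-hour parenthesis from the *possible* row in section 7.2.
- Add to 7.2 that time since the last monthly dose is not by itself a reason to choose *unlikely*.
- Reconcile the table with the suspected-reaction reporting in 3.3, the recording criterion in 7.3.1 and the description of ongoing symptoms in 8, and carry the wording into the online AR/SAE form.

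A replacement window running from the first dose until an interval after the last is not advisable. It would make almost every on-study event possible on timing alone and leave timing with no discriminating value.

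The cost is one table cell, one sentence, help text on the form and a short training note. Somewhat more non-serious events will be recorded.
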